16.0 STATISTICAL DESIGN AND ANALYSES

A formal Statistical Analysis Plan (SAP) will be written for this study but the general design and statistical strategies are described below.

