However, we expect there will be more subjects with 24 negative UDS than would be expected based on the Poisson distribution (ceiling effect). Also, there may be more subjects with 0 negative UDS than determined by the Poisson distribution (floor effect). Given the presence of ceiling and floor effects a more flexible model is needed than the hurdle model or zero-inflated Poisson model that would typically be used with count data with floor effects. Therefore, a beta-binomial regression model is anticipated⁷⁰. In this approach, the number of negative UDS is modeled as the number of 'successes' in 24 trials where each trial can result in a success or failure (UDS negative or positive) outcome. The probability of success across subjects is modeled with the beta distribution which is flexible enough to allow for a 'U' shaped distribution with both ceiling and floor effects or only ceiling effects depending on which parameters of the beta distribution are selected. The model will have terms for time, treatment group, treatment group by time interaction, baseline measure of the outcome, and any covariates. The primary hypothesis will be tested by significance of the main effect or interaction effect⁷¹.

- b. Self-reported days of MA use during Weeks 1-12 (score range 0-84) will be analyzed using TLFB data that will be collected in Weeks 1-12 with days of use counted over that period. Count data typically follow a Poisson or Negative Binomial distribution. However, we expect that there will be more participants with zero positive UDS than expected under these distributions (floor effect). We do not expect ceiling effects for this outcome. We will deal with the excess zeros using a hurdle model in which it is assumed that all participants have the potential to use drugs but "resistance" to drug use, or a hurdle, must be overcome before drugs are used. The existence of the hurdle results in an excess of participants with zero positive UDS⁷². The hurdle model will contain a random participant effect, treatment group (buprenorphine vs control), baseline number of use days (in the 30 days before written consent) and any other covariates needed to improve balance between the intervention and control groups. If the data are not zero-inflated, Poisson regression will be used.

2. *Measures of opioid use:* both

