number of male sexual partners, (f) Self-reported number of episodes sharing needles, and (g) Self-reported number of episodes sharing injection equipment and paraphernalia will each be analyzed using a repeated measures mixed effects model for count data outcomes. If zero-inflation is observed a zero-inflated poisson, negative binomial, or hurdle model will be used depending on which model best fits the data. However, if an outcome has low counts, we may collapse it into a binary (presence/absence) outcome. If the data are very sparse, we may collapse across weeks and use a logistic regression model.

7. *Measures of functioning:*

- a. Changes in self-reported assessment of Quality of Life (QoL) at Week 1 and Week 12 will be analyzed using repeated-measures mixed-effects model, with terms for time, treatment group, treatment group by time interaction, baseline measure of the outcome, and any covariates. Person effects will be random and all other effects fixed.
- b. Self-reported overall functioning as measured by the Treatment Effectiveness Assessment (TEA) at Week 12 will be analyzed using analysis of covariance.
8. *Measures of adverse events:* both (a) Number and severity of adverse events reported during Weeks 1-12 and (b) Number and outcomes (non-fatal, fatal) of overdose events during Weeks 1-12 will be analyzed using Chi-square tests for each measure of AEs.
9. Self-reported measures of alcohol, tobacco and other drug use on TLFB at Weeks 1, 5, 9, and 12, and UDS results of other substance use not quantified for primary or secondary outcomes will be analyzed using a repeated-measures mixed-effects model for continuous outcome (amount of use) or binary outcome (presence/absence of use). The models will have terms for time, treatment group, treatment group by time interaction, baseline measure of the outcome, and any covariates. Person effects will be random and all other effects fixed.
10. Urinalysis results indicating a new chlamydia or gonorrhea diagnosis at Week 12 will be analyzed using a logistic regression with the presence of a Week 12 diagnosis as the outcome and treatment group and other covariates and predictors.
11. IGT at screening as a predictor of treatment response will be analyzed using the primary outcome analysis being repeated with the addition of terms for baseline IGT performance and IGT by time interaction.

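### Secondary outcome 1b (self-reported MA-use days) falls back to Poisson regression with no stated protection against overdispersion, and has no rule for days not covered by TLFB under either model

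*Combined protocol and SAP*

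**What the plan says.** Section 16.3.2, item 1b, takes TLFB data "collected in Weeks 1-12 with days of use counted over that period". It remarks: "Count data typically follow a Poisson or Negative Binomial distribution". It expects excess zeros, though it words that expectation in terms of positive urine screens rather than days of use. It then specifies: "The hurdle model will contain a random participant effect, treatment group (buprenorphine vs control), baseline number of use days", plus any covariates needed for balance. The whole of the alternative is one sentence: "If the data are not zero-inflated, Poisson regression will be used".

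Items 2b and 3b (opioid-use days and co-use days) refer back to 1b. The sandwich estimator is specified in Section 16.3.1 for the primary GEE only. Section 16.7 imputes missing urine results as use in the primary analysis; for secondary outcomes it promises sensitivity analyses where appropriate, without detail. Section 16.4 applies no multiplicity adjustment to secondary outcomes. Section 16.0 says a formal SAP will follow and that "the general design and statistical strategies are described below".

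**The concern.** There are two separate gaps.

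**Variance.** Poisson regression fixes the variance of a person's count at its mean. Use days out of 84 will usually vary more than that, because people differ in how often they use. The hurdle model handles this through its random participant effect. The fallback does not say whether that effect, or the baseline covariate, remains. If it is programmed literally, the standard error is too small and chance differences are declared significant too often.

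**Days covered.** Item 1b gives no denominator. If a participant leaves at day 40, the remaining 44 days contribute no use to a raw count, so they act as abstinent days. This is the opposite of the rule for the primary outcome, and it favours the arm that loses more people. Robust errors do not cure it, and it affects the hurdle model as much as the fallback.

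At stake is one of six secondary outcomes, tested at an unadjusted level. The primary analysis, sample size and visit schedule are not touched.

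**Working it through.** **Inputs from the documents.** N = 246 at 1:1 (Sections 16.1.3 and 16.2), so 123 per arm. Score range 0-84 (Section 7.2). Baseline use on at least 18 of 30 days (Section 8.1, criterion 5). The 5% two-sided level is stated for the primary outcome and assumed here for 1b. The plan states no SD, dropout rate or operating characteristic for 1b, so there is no figure of its own to reproduce.

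**Assumed.** Mean share of days with use p; between-person SD s of that share; no treatment effect; all days reported; one count per person.

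**Step 1: closed form.** With beta-binomial counts out of 84, rho = s²/[p(1−p)] and variance/mean is phi = (1−p)(1 + 83·rho). A Wald test using Poisson variance has true size 2[1 − Φ(1.96/√phi)].

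- p = 0.6, s = 0.15 (12.6 days): rho = 0.0225/0.24 = 0.094; phi = 0.4 × 8.78 = 3.51; 1.96/1.874 = 1.046; size 30%.
- p = 0.5, s = 0.20 (16.8 days): rho = 0.16; phi = 0.5 × 14.28 = 7.14; 1.96/2.672 = 0.734; size 46%.
- p = 0.85, s = 0.15: rho = 0.176; phi = 0.15 × 15.65 = 2.35; 1.96/1.532 = 1.279; size 20%.
- p = 0.6, s = 0.05 (4.2 days): rho = 0.0104; phi = 0.4 × 1.865 = 0.75; 1.96/0.864 = 2.27; size 2%.

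The break-even is phi = 1, which at p = 0.6 means rho = 1.5/83 = 0.018. Plain Poisson is conservative only if participants are nearly alike.

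**Step 2: simulation** (123 per arm, null; 4,000 replicates for plain and robust Poisson, 600 for the other two models).

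| Analysis | Setting | Rejection at nominal 5% |
|---|---|---|
| Plain Poisson, unadjusted | SD 13-17 days, p 0.5-0.85 | 21-46% |
| Plain Poisson, unadjusted | SD 8 days, p 0.5 to 0.9 | 19% down to 5% |
| Plain Poisson, unadjusted | SD 4 days, p 0.5 to 0.9 | 4.4% down to 0.1% |
| Random participant effect kept | SD 8-17 days | 3.2-6.8% |
| Negative binomial | SD 8-17 days | 1.3-6.0% |
| Robust Poisson | all 24 settings | 4.4-5.7% |

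**Step 3: baseline adjustment** (1,500 replicates, SD 13-17 days). Plain Poisson falls to 15-33% when baseline and outcome correlate at about 0.5, and to 9-25% at about 0.7. Together that is 9-33%. Adjustment helps but does not restore 5%.

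**Step 4: is the fallback reachable?** In the first row of the table, fewer than 5% of simulated trials contained even one participant with zero use days. With person-level totals, then, the hurdle part may well not be needed. If records were weekly, zero weeks could arise, so use of the fallback is plausible rather than certain.

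**Step 5: uncovered days.** Assume dropout on a day uniform over 7-83 (mean 45). Expected covered days per person are:

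- 20% dropout: 0.80 × 84 + 0.20 × 45 = 76.2
- 30% dropout: 0.70 × 84 + 0.30 × 45 = 72.3
- 35% dropout: 0.65 × 84 + 0.35 × 45 = 70.35

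With no true effect, the raw-count ratio is 72.3/76.2 = 0.949 or 70.35/76.2 = 0.923. Simulation, including cases where heavier users drop out more, gives 0.939-0.949 and 0.908-0.924. With log covered days as offset it gives 0.986-1.001. Scoring uncovered days as use gives 1.003-1.044, an error in the other direction.

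**The case against.** The strongest reply is that the fallback is triggered only by absence of zero-inflation, so the natural reading drops the hurdle part and keeps the random effect and baseline days. On that reading the test holds its level (3-7%), and one clarifying clause is enough. This stands as a reading. It does not remove the gap, because the terms are attached in writing to the hurdle model alone, and Section 16.0's promise of a fuller SAP does not stop this sentence being copied into it as it is.

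On uncovered days, TLFB asks about every day since the previous assessment (Section 11.4.2), so missed visits are recovered. Participants off medication are encouraged to keep attending (Section 10.10). A Week 16 TLFB is scheduled, although 1b's wording leaves unclear whether it may fill earlier days. These points limit the loss to days after effective dropout. No document predicts unequal dropout.

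Four stronger readings are tempting but unsupported:

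- That the planned 1b test has a 20-45% error rate. That range is unadjusted and covers only the upper half of an assumed SD range.
- That Section 16.6 shows the authors guarding against overdispersion elsewhere and forgetting it here. That rule reads "If zero-inflation is observed a zero-inflated poisson, negative binomial, or hurdle model will be used depending on which model best fits the data", so negative binomial is conditional on zero-inflation and is not a fallback without it.
- That the positive-urine wording undermines "We do not expect ceiling effects for this outcome". The slip concerns the floor and says nothing about the ceiling.
- That the same error rates apply to 2b and 3b. Entry there can rest on as few as two opioid-use days in 30, with opioid-negative urines required, so excess zeros and the hurdle model are more likely. Those outcomes were not simulated.

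**Conclusion.** The point holds as an under-specified rule that, taken literally, can give an invalid test of 1b. With one count per person and an assumed between-person SD of 13-17 days, plain Poisson has a type I error of about 20-45% unadjusted and about 9-33% after baseline adjustment. It is at or below nominal if the SD is about 4 days, and about 3-7% if the random effect is retained. Since the documents give no SD, these are ranges under assumption rather than a prediction.

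The uncovered-days gap is independent of the variance question and applies to the hurdle model too. Its size, a rate ratio of about 0.92-0.95 under no effect, depends entirely on the assumed 30-35% versus 20% dropout; with equal dropout the raw ratio is about 1.

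Nothing here bears on the primary result. The point should be fixed before the SAP is final, with medium confidence that it would matter in practice.

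**What to change.** Replace the fallback sentence in 1b with wording such as: *When zero-inflation is absent, 1b will be analysed by Poisson regression with robust (sandwich) standard errors, one record per participant, adjusted for baseline use days.* Negative binomial, or an explicitly retained random participant effect, is an acceptable alternative; name one. Robust errors come first because at a true ratio of 0.92 they had the highest simulated power in the three settings tried (for example 71% against 58% for negative binomial and 52% for the random effect, at mean 85% and SD 17 days).

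For 1b as a whole, whichever model is used:

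- Account for days covered by TLFB in Weeks 1-12, with log covered days as offset in the count part, and say whether Week 16 recall may count as coverage.
- Add a sensitivity analysis scoring uncovered days as use.
- Change *zero positive UDS* to *zero days of use*.

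For 2b and 3b, carry over only the overdispersion protection, for use if their fallback is reached. Decide the scoring of uncovered days there separately.

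The cost is SAP wording and code. The 1b interval widens where use days vary between people. The offset assumes that uncovered days resemble covered ones, which Section 16.7's own doubt about missing-at-random makes uncertain; hence the sensitivity analysis. Sample size, visits and the primary analysis do not change.

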16.4 Significance Testing

The primary outcome will be evaluated using a two-sided test with a type I error rate of 5%. There are numerous secondary outcomes; however, multiple comparisons will not be adjusted for since these are not part of the study's primary objective.

16.5 Interim Analysis

When at least 50% of the final sample has attained endpoint assessment (i.e., Week 12), a sample-size re-estimation will be performed. Figure 16.2 shows sample sizes expected at the time of sample-size re-estimation, assuming recruitment is constant over time. The blue line in Figure 16.2 depicts recruitment, while the red line depicts attainment of primary endpoint. As noted previously, recruitment is anticipated to take 18 months to attain a sample size of 246. Primary endpoint data accumulates starting at month 3 and will terminate at month 21. Since missing UDS data will be assumed as MA-positive, the primary endpoint is always observed. Half of the 246 primary endpoints (i.e., 123 endpoints) will be attained at month 12, at which time a sample size re-estimation will be conducted. We expect at that time to have recruited 67% of our final sample size, or 164 of 246 participants.

Figure 16.2: Sample sizes during sample-size re-estimation.

The objective of sample size re-estimation is not to re-calculate the sample size using a treatment effect different from that posited during trial design, but rather to discover whether nuisance parameters, such as the site effect or the within-subject autocorrelation, were mis-specified, thus rendering invalid the original sample size calculation. Given that the study is double-blinded, only data from participants in the control (i.e., PBO-Inj) arm will be used in the re-estimation to preclude the need to break the blind during the conduct of the study. Modified bootstrapping will also be used for the sample size re-estimation as was done for the original sample size calculation. The unit of bootstrapping will be the entire participant history, together with the participant's site. Missing observations will be imputed to be MA-positive. Only control participants completed will be used in the sample size re-estimation bootstrap. There will be many bootstrap iterations. After each one, there will be a simulated test of the null hypothesis. The proportion of iterations in which the simulated two-sided test is significant at level 0.05 will be taken as the prediction of final power under the design alternative.

Participants with the endpoint assessment in the control arm will be randomly chosen with replacement to attain the desired sample size in the simulated control arm. In each bootstrap iteration, the entire simulated control arm will be recreated *de novo*. That is, the already-enrolled control participants will not be maintained together as a group within the simulated set of control participants.

To choose participants for the simulated treated arm, we will perform biased bootstrap sampling of the already-completed patients in the control arm. The method for performing biased bootstrap sampling will be discussed in the standalone Statistical Analysis Plan, but basically, some control patients will be preferentially chosen to allow $Pr(\text{success})$ in the simulated treated arm to be as desired. Biased bootstrap sampling will allow us to calculate power under the design alternative. More specifically, computer code will (1) estimate $\hat{p} = Pr(\text{success})$ in the control arm, (2) use biased bootstrap sampling of the participants in the control arm to force their mean simulated probability of success to be $\hat{p} + \Delta$, where Δ is the design treatment effect, namely 0.10. This can be done without explicitly calculating the observed treatment effect or revealing it to trial personnel.

The results of the sample size re-estimation will be presented to the DSMB, who will make recommendations to the Sponsor who will then decide what action, if any, should be taken. We anticipate re-estimation will be used only to increase trial recruitment, not to curtail it.

16.6 Exploratory Analysis

Exploratory analyses include:

1. *Measures of MA subjective effects*: both (a) MA withdrawal, as measured by scores on the Amphetamine Cessation Symptom Assessment during Weeks 1-12 and (b) self-reported MA craving as measured by the Visual Analog Craving Scales (VAS) during Weeks 1-12 will be analyzed by repeated-measures mixed-effects model. The model will have terms for time, treatment group, treatment group by time interaction, baseline measure of the outcome, and any covariates. Person effects will be random and all other effects fixed.

2. *Measures of opioid subjective effects*: All measures, (a) Observer rating of opioid withdrawal as measured by the Clinical Opiate Withdrawal Scale (COWS) on the day of randomization; each subsequent visit during induction in Week 1, if needed; prior to each injection in Weeks 1, 5, and 9; and at Week 12 ; (b) Self-reported rating of opioid withdrawal as measured by the Subjective Opiate Withdrawal Scale (SOWS) on the day of randomization; each subsequent visit during induction in Week 1, if needed; prior to each injection in Weeks 1, 5, and 9; and at Week 12; (c) Self-reported opioid craving, as measured by Visual Analog Craving Scales (VAS), during Weeks 1-12 will each be analyzed using repeated-measures mixed-effects models, with terms for time, treatment group, treatment group by time interaction, baseline measure of the outcome, and any covariates. Person effects will be random and all other effects fixed.
3. *Self-reported craving for MA and opioid co-use*: As measured by Visual Analog Craving Scales (VAS), during Weeks 1-12 will each be analyzed using repeated-measures mixed-effects models, with terms for time, treatment group, treatment group by time interaction, baseline measure of the outcome, and any covariates. Person effects will be random and all other effects fixed.
4. *Measures of mood, pain and stress*: All measures, (a) Changes in self-reported depressive symptoms as measured by the IDS-SR during Weeks 1-12, (b) Changes in self-reported anxiety symptoms as measured by the GAD-7 during Weeks 1-12, (c) Changes in self-reported mood symptoms as measured by the CAST-IRR during Weeks 1-12, (d) Changes in self-reported anhedonia as measured by the DARS during Weeks 1, 5, 9, and 12, (e) Changes in self-reported pain as measured by the P-FIBS during Weeks 1-12, and (f) Changes in self-reported stress as measured by the PSS during the Weeks 1, 5, 9, and 12 will each be analyzed using repeated-measures mixed-effects models, with terms for time, treatment group, treatment group by time interaction, baseline measure of the outcome, and any covariates. Person effects will be random and all other effects fixed.
5. *Retention*, defined as the number of visits (0-24) present and providing urine drug samples during Weeks 1-12 will be analyzed similarly as described for the secondary outcome.
6. *Measures of Infectious disease control, incidence, and risk*:
 - a. Defined as the biomarkers measured at Week 12, remaining HIV-negative for those that started the trial HIV-Negative and remaining HCV-negative for those that started the trial HCV-Negative, will be analyzed using logistic regression with HIV status and HCV status as the outcomes, respectively, and treatment group and other covariates as predictors.
 - b. Self-Reported HIV transmission risk behaviors measured at Weeks 1, 6 and 12, defined as (a) Self-reported number of new sexual partners, (b) Self-reported number of sexual partners with condomless sex who are serodiscordant or unknown serostatus, (c) Self-reported number of sexual partners with condomless sex with partners who are serodiscordant or unknown serostatus with whom illicit substance were used (chemsex), (d) For men, self-reported

number of male sexual partners, (f) Self-reported number of episodes sharing needles, and (g) Self-reported number of episodes sharing injection equipment and paraphernalia will each be analyzed using a repeated measures mixed effects model for count data outcomes. If zero-inflation is observed a zero-inflated poisson, negative binomial, or hurdle model will be used depending on which model best fits the data. However, if an outcome has low counts, we may collapse it into a binary (presence/absence) outcome. If the data are very sparse, we may collapse across weeks and use a logistic regression model.

7. *Measures of functioning:*

- a. Changes in self-reported assessment of Quality of Life (QoL) at Week 1 and Week 12 will be analyzed using repeated-measures mixed-effects model, with terms for time, treatment group, treatment group by time interaction, baseline measure of the outcome, and any covariates. Person effects will be random and all other effects fixed.
- b. Self-reported overall functioning as measured by the Treatment Effectiveness Assessment (TEA) at Week 12 will be analyzed using analysis of covariance.
8. *Measures of adverse events:* both (a) Number and severity of adverse events reported during Weeks 1-12 and (b) Number and outcomes (non-fatal, fatal) of overdose events during Weeks 1-12 will be analyzed using Chi-square tests for each measure of AEs.
9. Self-reported measures of alcohol, tobacco and other drug use on TLFB at Weeks 1, 5, 9, and 12, and UDS results of other substance use not quantified for primary or secondary outcomes will be analyzed using a repeated-measures mixed-effects model for continuous outcome (amount of use) or binary outcome (presence/absence of use). The models will have terms for time, treatment group, treatment group by time interaction, baseline measure of the outcome, and any covariates. Person effects will be random and all other effects fixed.
10. Urinalysis results indicating a new chlamydia or gonorrhea diagnosis at Week 12 will be analyzed using a logistic regression with the presence of a Week 12 diagnosis as the outcome and treatment group and other covariates and predictors.
11. IGT at screening as a predictor of treatment response will be analyzed using the primary outcome analysis being repeated with the addition of terms for baseline IGT performance and IGT by time interaction.

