16.1.3 Randomization and Factors for Stratification

Participants will be randomized in a 1:1 ratio to BUP-Inj or PBO-Inj, using a permuted block design with random block sizes and stratified by enrolling site. A separate randomization plan will be developed with additional details regarding treatment allocation. Given that the study is double-blind, only certain staff at the DSC and CCC will be able to access individual treatment assignments and detailed information contained in a separate Blinding Management Plan.

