16.2 Rationale for Sample Size and Statistical Power

A sample size of 246 was chosen for this study to provide 90% power to detect a statistically significant difference between the two treatments. Power was based on an effect size derived from the proportion of MA-negative urines during the last 4 weeks of Phase I of the ADAPT-2 study (CTN-0068) comparing the active treatment arm to the placebo arm. Imputing all missing data as positive, the relevant proportions in ADAPT-2 were 0.17 and 0.07 in the treated (AMC) and control (PBO) arms respectively, so we take the treatment effect of interest for MURB to be a risk difference of 0.10 corresponding to an odds ratio of 2.72. This outcome from the ADAPT-2 study was chosen because it was believed to be the most comparable available result using this substance-using population to the BUP-Inj outcome for this study.

To simulate data for CTN-0110, we first imputed all missing ADAPT-2 visits as UDS-positive for MA, then bootstrapped the ADAPT-2 participants, keeping the participant's site and visits together, thus respecting whatever temporal and site-dependent correlations might exist in the data. We assumed equal treatment allocation. To draw bootstrap samples of size N, we bootstrapped differently under null and alternative hypotheses as follows:

- Null: We treated the two simulated treatments the same way: for each of the N/2 simulated participants receiving that treatment, we flipped a fair coin to decide which ADAPT-2 arm (109 AMC and 294 PBO) to draw it from, and then drew it randomly with replacement from that arm.

- Alternative: For AMC, we drew $N/2$ observations randomly with replacement from the 109 AMC patients. For PBO, we drew $N/2$ observations randomly with replacement from the 294 PBO patients.

[figure not shown]
To simulate 2 UDS per week we used all 8 visits of a participant in order. The model under which we performed the power analysis is the same as that to be used for the primary analysis, discussed in Section 16.3.

Simulated power for the generalized estimating equation⁶⁹ is shown as a function of total N ($N/2$ in each arm) in Table 16.1 and in Figure 16.1, in which the total sample size required for power (0.8, 0.9) is interpolated from the simulated data using a logistic function, and estimated to be (182, 246).

Table 16.1: Simulated power for the GEE as a function of total N ($N/2$ in each arm)

Total N	Power
100	0.55
150	0.74
200	0.84
250	0.91
300	0.96
350	0.97

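### The Section 16.6 mixed models for repeated scales name no within-person dependence beyond a person effect, so the treatment-by-time test can reject too often on the weekly scales

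*Combined protocol and SAP*

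**What the plan says.** Section 16.6 item 1 (ACSA and methamphetamine craving) sets out a repeated-measures mixed model: "The model will have terms for time, treatment group, treatment group by time interaction, baseline measure of the outcome, and any covariates". Items 2 to 4 repeat this, "with terms for time, treatment group, treatment group by time interaction, baseline measure of the outcome, and any covariates", for opioid withdrawal and craving, co-use craving, and mood, pain and stress. Each item closes with the same rule on the random part: "Person effects will be random and all other effects fixed". Items 7a and 9 use it too.

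The schedules differ:
- **Weekly, 12 values:** ACSA, three craving VAS, IDS-SR, GAD-7, CAST-IRR and P-FIBS; for example "a) Changes in self-reported depressive symptoms as measured by the IDS-SR during Weeks 1-12".
- **About four visits:** DARS and PSS, for example "d) Changes in self-reported anhedonia as measured by the DARS during Weeks 1, 5, 9, and 12"; also COWS and SOWS, which add induction visits where needed.
- **Two visits:** item 7a, "Changes in self-reported assessment of Quality of Life (QoL) at Week 1 and Week 12 will be analyzed using repeated-measures mixed-effects model".

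Section 16.6 does not say whether time is linear or categorical, gives no residual covariance or robust variance, and does not say which model term will be reported. Section 16.4 states a 5% level for the primary outcome only. Section 16.0 says that a formal SAP will follow.

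**The concern.** On its plain reading, the rule gives each participant a random intercept and nothing more. Week 1 is then assumed to be as strongly correlated with Week 12 as with Week 2. Scores for mood, craving and pain taken weekly in the same person commonly drift or correlate more closely at short lags. If they do so here, the residual variance understates how much person-level slopes vary, and the treatment-by-time standard error is too small.

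The plan does not treat dependence this lightly elsewhere. For the urine outcome, Section 16.3.1 uses an AR(1) working correlation with a sandwich estimator, and Section 16.5 lists within-subject autocorrelation as a nuisance parameter to re-check. Neither protection appears in Section 16.6.

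At stake are statements that mood, craving, withdrawal or pain followed different courses in the two arms. Mood matters to the trial's rationale: Section 4.1 argues from a kappa-antagonist effect and mentions reports of dysphoria and stress.

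**Working it through.** The plan states no type I error for these models, so there is no figure of its own to reproduce.

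**Inputs from the documents.** "A sample size of 246 was chosen for this study to provide 90% power to detect a statistically significant difference between the two treatments" and "Participants will be randomized in a 1:1 ratio to BUP-Inj or PBO-Inj" give 246/2 = 123 per arm. Visits are Weeks 1-12, or 1, 5, 9 and 12, or 1 and 12. The random part is a person effect only.

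**Assumed inputs.** Two-sided 5% level; total variance 1, with 0.5 from the person intercept and 0.5 residual; complete data for the closed form. Two departures from a pure random intercept are tried:
- AR(1) residuals with correlation ρ.
- Person-specific linear slopes, where k is the variance of the Week 1 to Week 12 change divided by the residual variance. The slope variance per week is then 0.5k/121.

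**Formula, linear time.** Let c be the centred visit weeks, S = c'c, V the true within-person covariance, m the number of visits and M the centring matrix.
- The model's residual variance settles at s² = trace(MVM)/(m − 1), so the model-based slope variance is proportional to s²/S.
- The true slope variance is proportional to c'Vc/S².
- Their ratio is R = (c'Vc/S)/s². The actual size is 2[1 − Φ(1.96/√R)].

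Sample size cancels from R, so enrolling more people does not help.

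**Worked case, 12 weeks, slopes with k = 1.** S = 143. c'Vc/S = 0.5 + (0.5/121)(143) = 1.091. s² = 0.5 + (0.5/121)(143/11) = 0.554. R = 1.97, 1.96/√1.97 = 1.396, size 16.3%.

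**Worked case, 12 weeks, AR(1) with ρ = 0.5.** c'Vc/S = 1.028, s² = 0.424, R = 2.42, 1.96/√2.42 = 1.259, size 20.8%.

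**Categorical time.** The Wald statistic is a weighted sum of chi-square(1) variables, with weights λ/s², where λ are the m − 1 non-zero eigenvalues of MVM. It is compared with the chi-square critical value on m − 1 degrees of freedom (11 for weekly scales).

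| True structure | 12 visits, linear | 12 visits, categorical | 4 visits, linear | 4 visits, categorical |
|---|---|---|---|---|
| Compound symmetry | 5.0% | 5.0% | 5.0% | 5.0% |
| AR(1) 0.3 | 12.9% | 6.1% | 5.2% | 5.0% |
| AR(1) 0.5 | 20.8% | 7.9% | 6.1% | 5.0% |
| AR(1) 0.7 | 30.3% | 10.2% | 8.7% | 5.4% |
| AR(1) 0.9 | 40.3% | 12.7% | 13.9% | 6.4% |
| Slopes, k = 0.25 | 8.1% | 5.1% | 6.1% | 5.1% |
| Slopes, k = 1 | 16.3% | 5.7% | 8.8% | 5.2% |
| Slopes, k = 2 | 23.9% | 6.7% | 11.5% | 5.6% |

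**Two visits (item 7a).** There is only one within-person contrast, so c'Vc/S equals s², R = 1, and the size is 5% whatever V is.

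**Time-averaged effect.** With balanced data the random-intercept model takes its variance from the spread of person means, which is correct for any V. Simulated size was 4-5%.

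**Simulation with a baseline covariate.** REML fits of the random-intercept model on 12 weekly values with 4% dropout per week gave 7.7-38.9% for linear time across the departures tried, and 4.5% under compound symmetry. The categorical test gave 6.0-12.8% with dropout and 5.6-15.4% without. Those came from 500 runs each; at 15.4% the Monte Carlo standard error is √(0.154 × 0.846/500) = 1.6 points.

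**After correction.** An unstructured-covariance test and a test on person-level slopes gave 4.3-5.7% in every scenario. With complete data, the slope test is in effect what a sandwich standard error does for the linear interaction.

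**The case against.** The strongest reply is that this is a gap in specification, in analyses labelled exploratory. No significance level or decision rule attaches to them, a formal SAP is still to come, and nothing in Section 16.6 makes the interaction the reported result. All of that stands, and it limits the consequence. It does not remove the point: a SAP that carries the sentence over inherits the problem, and covariance and time coding are better fixed before data are seen.

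Several stronger readings are tempting, and the documents do not support them.
- **That the plan's tests reject a true null 8-40% of the time.** The documents give no autocorrelation or slope variance for any scale and do not say that time is linear. The 40% figure needs linear time and AR(1) of 0.9 on top of a random intercept.
- **That the plan excludes serial correlation.** It leaves residual covariance unstated within a model called repeated-measures. Not specified is the accurate description.
- **That treating time as fixed is the fault.** Fixed time is ordinary. What is missing is a person-by-time effect, a residual structure or a robust variance.
- **That only compound symmetry protects.** Sphericity is enough for the categorical test, and two visits are always safe.
- **That false trajectory differences should be expected on many scales.** Over eight weekly scales a true 5% test gives 8 × 0.05 = 0.4 expected false interactions. At AR(1) of 0.5 this becomes 8 × 0.208 = 1.7 with linear time, but only 8 × 0.079 = 0.6 with categorical time.
- **That every item using the sentence is affected.** Item 7a is not. The binary models of item 9 were not examined.

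**Conclusion.** The concern holds in a conditional form. As written, the only within-person dependence stated for the continuous scales of items 1-4 is a person effect, and a model-based treatment-by-time test on that footing is anti-conservative whenever slopes vary between participants or correlation decays appreciably between visits. The material exposure is on the eight weekly scales with linear time: about 13-40% for AR(1) of 0.3-0.9, and about 8-24% for k from 0.25 to 2. It is much smaller with categorical time (about 5-13%) and for DARS, PSS, COWS and SOWS (about 5-14% linear, 5-6% categorical).

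These ranges rest on assumed correlations, an intercept share of one half and a 5% level, none of which the documents supply for these scales. The time-averaged treatment effect keeps its size, and this sentence does not govern the primary or secondary analyses. It is a worthwhile, low-cost improvement and no threat to the trial's main conclusion.

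**What to change.** In Section 16.6 items 1-4 and the continuous outcomes of item 9, and in the SAP:
- State how time is coded.
- Either keep the random person effect and use empirical (sandwich) standard errors, or replace it with an unstructured within-person covariance and Kenward-Roger degrees of freedom. With the second option, name a fallback in advance, such as random intercept plus AR(1).
- For COWS and SOWS use the sandwich option, because the number of induction visits varies and an unstructured matrix is not well defined for that schedule.
- Name the time-averaged treatment contrast as the reported effect.

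Leave item 7a and the binary models of item 9 out of this change. The cost is wording only, with no effect on conduct, data collection or sample size. The downside is a few more covariance parameters and slightly wider intervals for the interaction.
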